9.8. ECG Assessments

An ECG will be performed at Screening, Baseline and within 1-2 hours of the last dose (3rd dose) of study drug and include the following parameters: QTc Interval, PR Interval, and QRS Duration. The grading scale for ECG evaluations is included in Table 4.

ECG change in overall interpretation from Baseline to Post Dose 3 will be shown in Table 30. Summaries of ECG results by severity for each parameter will be tabulated by timepoint and presented in Table 31.

Summary statistics of ECG results including mean, SD, median, min and max values by timepoint and change from baseline for the Post Dose 3 timepoint will be tabulated and presented by parameter for baseline and each post dose timepoint (Table 32). Data will be visualized using box plots showing the change from baseline at post Dose 3 (Figure 43, Figure 44, Figure 45).

Individual data listings of ECG results will be presented (Listing 17).

10. PHARMACOKINETICS

10.1. Analysis Population and Handling of Missing Timepoints

The pharmacokinetic analyses will be performed using the population of evaluable subjects as defined in Section 6.3.2.

Timepoints below the lower limit of quantification (LLOQ), referred to as below quantification limit (BQL), preceding the first PK concentration above the LLOQ will be imputed as 0. All other PK sample concentrations below the LLOQ will not be included in graphical displays or analyses.

All protocol deviations will be reviewed by the statistician. Major deviations such as receiving an incomplete dose, subject dosed but not meeting eligibility criteria, etc. may result in exclusion of a subject from PK analysis with approval from the sponsor. Statistical outlier concentrations will not be excluded from analysis unless associated with a protocol deviation that could plausibly explain the outlier.

Missing PK sample concentrations will not be imputed for the NCA.

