#### 8.2.3. Pharmacokinetic Blood and BAL Samples

An assay to measure ZTI-01 concentrations in plasma, BAL, and cell pellet samples and urea in plasma and BAL samples will be conducted at a central analytical lab using a validated LC-MS/MS bioanalytical assay. Timing of samples will be with respect to the start of each dose of study drug (pre-dose and postinfusion start, when applicable). The date and time of each PK sample and BAL collection will be recorded in the eCRF. Blood PK samples will be drawn for all subjects within the following windows: -10 to -1 minute for scheduled samples at pre-dose;  $\pm 5$  minutes for scheduled samples at 30 minutes, 1 hour 15 minutes, and 2 hours; +0-5 minutes from end of infusion for the scheduled sample at 1 hour; and  $\pm 15$  minutes for scheduled samples at 5, 8, and 12 hours. BAL samples for PK (fosfomycin and urea assays) will be obtained within +/- 15 minutes of the assigned sampling time.

Instructions for collecting, processing, storage, and shipping of plasma, BAL, and urine samples will be provided in the MOP.

Blood and BAL samples are summarized in Table 7.

Study day	Dosing	Blood sampling times*	BAL sampling times §
Day 1-2 Dosing ZTI-01 6 g IV infusion over 1 hour (+10 minute window)		All subjects: Pre-dose (-10 to -1 minutes), 30 minutes (during the 1-hour infusion), and 1 hour, 1 hour 15 minutes, 2, and 5 hours after the start of the first dose	No sampling
	Second dose: ZTI-01 6 g IV infusion over 1 hour (+10 minute window)	All subjects: Pre-dose (-10 to -1 minutes)	No sampling
	Third dose: ZTI-01 6 g IV infusion over 1 hour (+10 minute window)	All subjects: Pre-dose (-10 to -1 minutes), 30 minutes (during the 1-hour infusion), and 1 hour, 1 hour 15 minutes, and 2, 5, 8, and 12 hours after the start of the third (last) infusion of ZTI-01	Each subject: Complete a single bronchoscopy with BAL at one of the five sampling times: 30 minutes (during the 1-hour infusion), 1 hour 15 minutes, 2, 5, or 8 hours from the start of the third (last) infusion of ZTI-01
Day 2 At Discharge	No further dosing	All subjects: 12 hours after the start of the third (last) infusion of ZTI-01	No sampling
* Blood PK samp	les will be drawn for all subjects	within the following windows: -10	to -1 minutes for scheduled

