4. INVESTIGATIONAL PLAN

4.1. Overall Study Design and Plan

This is a Phase 1, open-label, multiple-dose trial conducted at a single center. The treatment period will consist of three 6 g doses of ZTI-01 as a 1 h IV infusion. A total of 30 enrolled subjects will be randomized. Six additional enrolled subjects will act as alternates. An evaluable subject is defined as a subject who receives all doses of ZTI-01, undergoes BAL at the randomized sampling timepoint with BAL return volume adequate for testing, and undergoes at least the one blood sampling timepoint that is concurrent with the assigned BAL sampling timepoint, with blood sampling volume that is adequate for testing. Subjects who initiate the Treatment Phase but are not evaluable will be replaced with an alternate at the sample BAL sampling timepoint.

Each subject will complete Screening, Baseline, Treatment, and Follow-up Phases. A diagram of the overall study design is shown in Figure 1. The Screening Phase will be conducted on an outpatient basis within 30 days of the Baseline Phase. The Baseline Phase will consist of admission to DEPRU on the day before the first dose (Day -1) for pre-dosing assessments. The Treatment Phase (Day 1 to Day 2) will include dosing 6 g of ZTI-01, administered as a 1-hour IV infusion, every 8 hours for a total 18 g in 3 doses, followed by post-treatment safety assessments, and BAL and blood sample collections for PK measurements. Each subject will undergo a single standardized bronchoscopy with BAL after the start of the last IV infusion of ZTI-01. Blood samples for PK measurements will be collected before each dose, up to 8 hours after the start of the first IV infusion of ZTI-01, and up to 12 hours after the start of the third IV infusion.

Subjects will remain in DEPRU during the Treatment Phase and will be discharged at least 12 hours after the start of the third IV infusion (if safety parameters are acceptable to the investigator). Safety assessments will be conducted during the entire Treatment Phase. The Follow-Up Phase will consist of a telephone interview on Day 3 for symptom-driven safety assessments.

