4.2. Discussion of Study Design, Including the Choice of Control Groups

As the main focus of this protocol is to evaluate the safety and pharmacokinetics of multiple doses of ZTI-01, there is no control group and all subjects receive the same dose of ZTI-01with the same PK blood collection timepoints. Subjects will be randomized to one of five BAL sampling timepoints with a total of 6 subjects assigned to each BAL sampling time.

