10.3.2. Noncompartmental Analysis Population AUC and Percent Penetration Estimation

The median concentrations of fosfomycin from the BAL sampling times will be used to estimate the population average AUC_{0-8} of plasma, ELF, and AM will be estimated using the Linear Up Log Down calculation method.

The ratios of population average AUC₀₋₈ of ELF-to-plasma and AM-to-plasma will be calculated to determine estimates of the percent penetration by dividing the AUC₀₋₈ for ELF or AM by the geometric mean Plasma AUC₀₋₈.

Summary statistics for all continuous PK measures and parameters will include mean, SD, min, max, median, coefficient of variation as a percent (CV%), GM, and geometric SD (GSD), unless otherwise specified. CV% will not be calculated for T_{max} and T_{last} since those variables are not log-normal.

The CV% will be calculated using the method for log-normally distributed data.:

 $CV\% = \sqrt{\exp(\sigma^2) - 1} * 100\%$, where σ^2 is the variance of the log-transformed data [5].

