- ¹PK blood samples will be collected at 15 timepoints: before (within 10 minutes) the first, second, and third doses of study drug, at 30 minutes (during infusion), 1 hour (within 5 minutes after the end of infusion), 1 hour 15 minutes, 2, and 5 hours from the start time of the first dose of ZTI-01, and at 30 minutes (during infusion), 1 hour (within 5 minutes after the end of infusion), 1 hour 15 minutes, 2, 5, 8, and 12 hours from the start time of the third (last) infusion of ZTI-01. Blood PK samples will be drawn for all subjects within the following windows: -1 to -10 minutes for scheduled samples at pre-dose; +/- 5 minutes for scheduled samples at 30 minutes, 1 hour 15 minutes, and 2 hours; +0-5 minutes after end of infusion for the scheduled sample at 1 hour; +/- 15 minutes for scheduled samples at 5, 8, and 12 hours. Actual times for dosing and sample will be recorded.
- ^m Bronchoscopy with BAL at 30 minutes (during the 1-hr infusion), 1 hr 15 minutes, 2, 5, or 8 hours from T0 (defined as the start time of the last [third] infusion of ZTI-01). BAL PK samples will be obtained within +/- 15 minutes of scheduled timepoint. Actual times for dosing and sample will be recorded.

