14.4 Pharmacokinetics

Table 35:Individual Concentrations and Summary Statistics by for Plasma Fosfomycin
Concentration (µg/mL) by Nominal Time - Dose 1

	Plasma Fosfomycin Concentration (µg/mL) by Nominal Time ^a After Dose 1											
Subject ID	0 h	0.5 h	1 ^b h	1.25 h	2 h	5 h	8° h					
SST.00101	X	х	X	X	х	х	х					
SST.00102	X	х	X	X	х	х	х					
SST.00102	X	х	X	X	х	х	х					
	x	x	х	X	х	х	х					
Statistics	X	х	X	X	х	х	х					
N ^d	X	х	X	X	х	х	х					
Mean	X.X	х	X	X	х	х	х					
SD	X.X	х	X	X	х	х	х					
Min	X.X	х	X	X	х	х	х					
Median	X.X	х	X	X	х	х	x					
Max	X.X	х	X	X	х	х	x					
CV% ^e	X	х	X	X	х	х	х					
GM	X	х	х	x	х	х	х					
GSD	Х	Х	x	X	x	X	x					

^a Times are relative to time of start of infusion of Dose 1.

^b 0-5 minutes from end of infusion for Dose 1.

^c Pre-dose for Dose 2

^d Number of data points used to compute the summary statistics. For calculation of summary statistics, BQL values were imputed as 0 if they did not come after a PK sample concentration that is above the LLOQ and treated as missing otherwise.

^e CV% = $\sqrt{(\exp(\sigma^2)-1)}$ * 100%, where σ^2 is the variance of the log-transformed data

		Plasma Fosfomycin Concentration (µg/mL) by Nominal Time ^a After Dose 3											
Subject ID	0 h	0.5 h	1 ^b h	1.25 h	2 h	5 h	8 h	12 h					
SST.00101	x	х	х	x	х	х	х	х					
SST.00102	х	x	х	x	х	x	х	х					
SST.00102	х	x	х	x	х	x	x	х					
	х	x	х	x	х	x	х	х					
Statistics	x	х	х	x	х	х	х	х					
N ^c	х	x	х	x	х	x	х	х					
Mean	x	х	х	x	х	х	х	х					
SD	х	x	х	x	х	х	x	х					
Min	х	x	х	x	х	x	х	х					
Median	х	x	х	x	х	x	х	х					
Max	х	x	х	x	х	x	х	х					
CV%	х	X	х	x	х	x	х	х					
GM	х	x	x	x	х	х	х	х					
GSD	х	х	х	х	х	х	х	х					

Table 36: Individual Concentrations and Summary Statistics by for Plasma Fosfomycin Concentration (µg/mL) by Nominal Time - Dose 3

^a Times are relative to time of dosing. Times are relative to time of start of infusion of Dose 3. Blood PK samples will be drawn within the following windows: -10 to -1 minute for scheduled samples at 0h; ±5 minutes for scheduled samples at 0.5h, 1.25h, and 2h; +0-5 minutes from end of infusion for the scheduled sample at 1h; and ± 15 minutes for scheduled samples at 5h, 8h and 12h.

^b 0-5 minutes from end of infusion for Dose 3.

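### Read literally, SAP 10.1's single BQL rule excludes below-LLOQ BAL and cell-pellet results, so any that occur would generally bias ELF or AM medians and percent penetration upward

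*SAP*

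**What the plan says.** SAP 10.1 handles BQL results in two sentences. A value "preceding the first PK concentration above the LLOQ will be imputed as 0"; for the rest, "All other PK sample concentrations below the LLOQ will not be included in graphical displays or analyses". Neither sentence says plasma, BAL or cell pellet. The footnote to the schedule of procedures (SAP Table 1) calls BAL samples PK samples: "BAL PK samples will be obtained within +/- 15 minutes of scheduled timepoint". The 10.1 wording can therefore cover them.

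The lung data are not serial. Protocol 8.2.3 (Table 7): "Each subject: Complete a single bronchoscopy with BAL at one of the five sampling times". SAP 4.1 agrees: "Each subject will undergo a single standardized bronchoscopy with BAL after the start of the last IV infusion of ZTI-01". SAP 4.2 puts five groups on the five times, "with a total of 6 subjects assigned to each BAL sampling time".

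SAP 10.3.2 builds the lung exposure from these groups: "The median concentrations of fosfomycin from the BAL sampling times will be used to estimate the population average" AUC0-8 in plasma, ELF and AM. Percent penetration is the ratio to plasma.

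The shells for plasma Tables 35 and 36 carry a second wording: "BQL values were imputed as 0 if they did not come after a PK sample concentration that is above the LLOQ", and missing otherwise. The shells for the ELF, AM and penetration results (Tables 41-43) carry no BQL rule. SAP 10.2 marks BQL in the plasma listing (Listing 25), but for BAL and cell pellet (Listing 27) it marks only out-of-window samples.

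**The concern.** The 10.1 rule suits a serial plasma profile, where a BQL value before the drug appears is close to zero and one in the tail adds little. A single lung sample has no profile around it. A BQL result there says that the concentration is low. Excluding it treats a low value as if it were absent, and the loss is not random, because only low measurements are removed.

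Replacement does not repair this. Evaluability (SAP 6.3.2) depends on adequate BAL return volume, not on a quantifiable result, so a subject with a BQL sample stays evaluable and is not replaced. The rule removes concentrations rather than subjects, so the plasma denominator keeps its values while the lung numerator loses its lowest ones. Percent penetration, a named outcome measure, would then tend to err in the drug's favour.

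**Working it through.** **Inputs.** From the documents: five BAL times (0.5, 1.25, 2, 5 and 8 h), six subjects at each (5 × 6 = 30), one sample per subject, a median per time, and linear-up log-down AUC. Not in the documents: the LLOQ in any matrix, expected ELF or AM concentrations, their variability, and any BQL rate. These are assumed below and varied. The plan states no figure for this point, so there is none to reproduce.

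**Step 1: what each wording does to a lone BQL lung sample.**

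| Wording | Test | Lone BQL BAL or pellet result |
|---|---|---|
| SAP 10.1 | Does it precede a quantifiable value? | No, so excluded |
| Tables 35-36 footnote (plasma) | Does it come after a quantifiable value? | No, so set to 0 |

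For a single sample the two give opposite handling.

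**Step 2: effect of exclusion on a median of six.** The full median is the average of the 3rd and 4th ordered values. Without the lowest value it is the 4th; without two, the average of the 4th and 5th; without three, the 5th. For log-normal values (200,000 simulated groups), the ratio to the full median is:

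| Lowest values dropped | CV 30% | CV 50% | CV 100% |
|---|---|---|---|
| 1 of 6 | 1.06 | 1.09 | 1.15 |
| 2 of 6 | 1.13 | 1.22 | 1.43 |
| 3 of 6 | 1.20 | 1.34 | 1.67 |

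**Step 3: averaged over the chance of BQL.** If each sample has probability q of being BQL, at least one of six is BQL with probability 1 − (1 − q)^6: 0.469 at q = 0.10 and 0.738 at q = 0.20. With CV 40-80% and no variation in dilution, the typical (median) rise in the timepoint median is:

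| q | Rise |
|---|---|
| 10% | 5-9% |
| 20% | 10-19% |
| 30% | 16-31% |
| 40% | 23-45% |

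**Step 4: urea dilution.** For ELF the LLOQ acts on the lavage fluid, before multiplication by plasma urea / BAL urea (SAP 3.3.1). A BQL lavage value is then not always the lowest ELF value. With an assumed dilution CV of 60% and q = 30%, exclusion raises the ELF median by 11-28% instead of 16-31%. Setting BQL to 0 in the same setting lowers it by about 9-11%. Neither rule is neutral.

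**Step 5: carry-through to AUC.** Assume relative medians of 0.6 at 0.5 h and 1.0 at 1.25 h, then first-order decline, over the 0.5 to 8 h span of the BAL times. The area is 0.75 × (0.6 + 1.0)/2 + (1 − C8)/k, with k = ln 2 / half-life.

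- Half-life 2 h (k = 0.3466, C8 = 0.0964): 0.600 + 2.607 = 3.207.
- Half-life 3 h (k = 0.2310, C8 = 0.2102): 0.600 + 3.418 = 4.018.

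Raising the 8 h median alone by a factor of 1.3 raises the area by 2-3%. Raising both the 5 h and 8 h medians by 1.3 raises it by 10-13%. Raising every median by one factor raises the area by that factor.

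If all six 8 h samples are excluded and the area stops at 5 h, it falls to 2.699/3.207 = 0.84 (half-life 2 h) or 3.108/4.018 = 0.77 (half-life 3 h).

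**The case against.** The strongest reply is that the harm is hypothetical. No document gives an LLOQ or an expected lung concentration, and if no lung sample is BQL nothing changes. That stands, and every percentage here is conditional.

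A second reply is that the SAP may not intend exclusion at all. The Table 35-36 footnotes would keep a lone BQL sample as 0. Those footnotes sit under plasma tables and do not govern ELF or AM, so 10.1 remains the only rule that reaches the lung data. What stands is that the two wordings conflict for single samples and the intent is open.

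A third reply points to existing safeguards. Tables 41-43 report N, Listing 27 gives individual results, SAP 10.2 promises discussion of special cases, and SAP 6.5 promises a summary of missing data. These might make an exclusion visible, but they do not change the estimate. Protocol 11.3 also refers PK details to a study-specific PK analysis plan, which is not among the documents. The trial is descriptive with no formal hypotheses, which limits the consequence.

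A reader might infer that the plan will delete low lung values and so will overstate penetration. The documents do not support that: they do not show that any lung sample will be BQL, and Step 5 shows that AUC0-8 can fall if a whole late timepoint is lost. A reader might also infer that ranking BQL results lowest settles the matter, since one or two of six would leave the median unchanged. That holds only where all samples share one limit. For ELF, a BQL lavage value with a high urea ratio can outrank a quantified one.

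**Conclusion.** The point holds conditionally. On its literal text SAP 10.1 excludes a BQL BAL or cell-pellet result, and no other provision corrects the median that follows. If such results occur, the ELF or AM median at that time, and percent penetration, are generally biased upward. Under log-normal values, six per time and CV 40-80%, the timepoint median rises about 5-9% at 10% BQL, 10-19% at 20% and 16-31% at 30%, somewhat less for ELF if dilution varies between subjects. The effect on AUC0-8 and penetration is smaller when only late times are affected. It is zero if nothing is BQL, and it can reverse if all 8 h samples are lost. The rule should be corrected before data lock; whether bias will arise in this trial cannot be known from the documents.

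**What to change.** In SAP 10.1, limit the present rule to plasma and give it the same wording as the Table 35-36 footnotes. Add a separate rule for ELF and AM:

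- Keep every BQL sample in the n for its BAL time, and treat it as lying between 0 and its LLOQ equivalent. For ELF that is the BAL LLOQ times the subject's own plasma-to-BAL urea ratio.
- Compute the timepoint median, AUC0-8 and percent penetration (Table 43) with all BQL samples at 0 and again with all at the LLOQ equivalent. Report the range where the two differ. Do not state that the ELF median is unaffected by up to two BQL results.
- With four or more of six BQL, the lower-bound median is 0 and the log-down rule is undefined, so state which trapezoid applies to that interval.
- Show the number BQL per timepoint in Tables 41-43, and flag BQL in Listing 27.

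The cost is a paragraph in the SAP, which Section 15 allows as an addendum before final data lock, and modest programming. The downside is that the ELF LLOQ equivalent differs by subject, and penetration may have to be reported as a range instead of a single figure.

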10.2. Dosing and Pharmacokinetic Sampling Summary

Subject infusion start and end times (including interruptions) for all infusions received will be presented for each subject (Listing 7). If infusion of the drug is interrupted, the start and end times of the interruption will be recorded. Regardless of the amount of study product received, all scheduled blood draws will be attempted to be collected within a window based on the start of the administration. Special cases that potentially affect the analysis will be discussed in the final report. Actual infusion duration will be used for NCA analysis. If actual infusion duration time is missing, a duration of 1 h will be imputed.

Fosfomycin concentrations in plasma will be listed by subject and infusion dose number, with BQL and out of sample time window samples indicated (Listing 25). Fosfomycin concentrations in BAL and cell pellet samples concentrations will be listed by subject with out of sample time window samples indicated (Listing 27). The listings will also indicate the nominal and actual time associated with the sample.

Nominal time is defined as the time in hours since the start of infusion of either Dose 1 or Dose 3 as shown below:

Dose 1

- Timing of PK sample = "Pre-Dose for Dose 1", Nominal Time = 0 h
- Timing of PK sample = "30 minutes after starting the first dose", Nominal Time = 0.5 h
- Timing of PK sample = "1 hour after starting the first dose", Nominal Time = 1 h
- Timing of PK sample = "1 hour 15 minutes after starting the first dose", Nominal Time = 1.25 h
- Timing of PK sample = "2 hours after starting the first dose", Nominal Time = 2 h
- Timing of PK sample = "5 hours after starting the first dose", Nominal Time = 5 h
- Timing of PK sample = "Pre-Dose for Dose 2", Nominal Time = 8 h

Dose 3

- Timing of PK sample = "Pre-Dose for Dose 3", Nominal Time = 0 h
- Timing of PK sample = "30 minutes after starting the third dose", Nominal Time = 0.5 h

- Timing of PK sample = "1 hour after starting the third dose", Nominal Time = 1 h
- Timing of PK sample = "1 hour 15 minutes after starting the third dose", Nominal Time = 1.25 h
- Timing of PK sample = "2 hours after starting the third dose", Nominal Time = 2 h
- Timing of PK sample = "5 hours after starting the third dose", Nominal Time = 5 h
- Timing of PK sample = "8 hours after starting the third dose", Nominal Time = 8 h
- Timing of PK sample = "12 hours after starting the third dose", Nominal Time = 12 h

Important protocol deviations related to dosing or PK sampling will be described. Possible bioanalytical errors and their effect on the PK analysis will be discussed.

10.3. Definition and Estimation of Individual PK Parameters

PK parameters will be estimated through a NCA using Phoenix® WinNonlin® version 8.0 or later (Pharsight Corporation, Cary, NC) using plasma concentrations collected after start of the first infusion. Actual post-dose time will be used for the estimation of PK parameters instead of nominal time.

Phoenix WinNonlin[®] NCA will use the following settings to compute parameters from serum and pulmonary PK data:

- Linear Up Log Down calculation method
- Uniform weighting
- IV Infusion
- Lambda Z Acceptance Criteria
- \circ Rsq_adjusted ≥ 0.90
- \circ Span \geq 3.0 half-lives
- \circ Includes at least 3 timepoints after T_{max}

10.3.1. PK Parameters

Cmax

Maximum concentration (C_{max}) for Dose 1 is defined as the maximum observed ZTI-01 concentration observed over all PK sample concentrations following Dose 1 and prior to Dose 2 and C_{max} for Dose 3 is defined as the maximum observed ZTI-01 concentration observed over all PK sample concentrations following Dose 3. It will be obtained from the **Cmax** parameter calculated by WinNonlin®. If there is no measurable concentration in the subject's PK profile, then C_{max} will be missing for that subject. C_{max} will be reported in units of $\mu g/mL$.

T_{max}

Time of maximum concentration (T_{max}) will be calculated separately for Dose 1 and for Dose 3. For Dose 1, T_{max} is defined as the time at which the maximum concentration occurs for PK sample concentrations following Dose 1 and prior to Dose 2. For Dose 3, T_{max} is defined as the time at which the maximum concentration occurs for PK sample concentrations following Dose 3. These will be obtained from the **Tmax** parameter calculated by WinNonlin®. If there is no measurable C_{max} in the subject's PK profile, then T_{max} will be missing for that subject. T_{max} will be reported in units of h.

λz

The elimination rate constant (λ_z) is defined as the first-order rate constant describing the rate of decrease of drug concentration in the terminal phase (defined as the region of the PK curve where absorption and distribution are no longer significant, and drug concentration follows first-order elimination kinetics). λ_z will be computed as the slope of a terminal region consisting of at least 3 successive points in the plot of log-transformed concentration data versus time. λ_z will be estimated using uniform weighting.

Time points used in the estimation of λ_z will be initially selected using the WinNonlin[®] automatic algorithm. Manually chosen time points may be used at the discretion of the PK analyst after examination of the automatically chosen points in the context of the semi-log profile. The set of points chosen will be that which maximizes the Pearson correlation (r) while satisfying the following. Computation of λ_z for a subject requires the use of at least three consecutive timepoints after T_{max} with evaluable concentrations above the LLOQ and for which the absolute value of the Pearson correlation (R^2) of log-transformed concentrations with time is greater than 0.8. If deemed necessary and appropriate, the observation collected at T_{max} may be used in the calculation of λ_z that use the timepoint at T_{max} will be clearly specified and justified in the analysis report. Drug concentrations used to calculate λ_z will be indicated in Listing 25. This parameter will be obtained from the Lambda_z parameter calculated by WinNonlin[®] and will be reported in units of /hours

t½

The apparent terminal elimination half-life $(t_{\frac{1}{2}})$ is defined as the time required for the drug concentration to decrease by a factor of one-half in the terminal phase. The apparent terminal elimination half-life $(t_{\frac{1}{2}})$ will be estimated as $\ln(2) / \lambda_z$. It will be obtained from the **HL_Lambda_z** parameter calculated by WinNonlin[®]. Half-life will be reported in units of h.

AUC

 $AUC_{(0-8)}$ for Dose 1 is defined as the area under the concentration-time curve from dosing for Dose 1 (Dose 1 Nominal Time=0 h) to 8 hrs post start of infusion, 12 hours post start of Dose 3 infusion, and the time of the last measured concentration, respectively.

 $AUC_{(0-8)}$ and $AUC_{(0-12)}$ will be estimated using the Linear Up Log Down calculation method. $AUC_{(0-last)}$ will be estimated using the Linear Up Log Down calculation method and obtained from the **AUClast** parameter calculated by WinNonlin[®].

 $AUC_{(0-\infty)}$ for Dose 3 is defined as the total area under the concentration-time curve from start of infusion for Dose 3 (Nominal Time=0 h) taken to the limit as the end time becomes arbitrarily large. $AUC_{(0-\infty)}$ will be estimated by adding the Dose 3 $AUC_{(0-last)}$ to an extrapolated value equal to the last measured concentration greater than the LLOQ divided by λ_z :

$$AUC_{(0-\infty)} = AUC_{(0-last)} + \frac{C_{last}}{K_e},$$

where C_{last} is the last measured concentration \geq LLOQ. AUC_(0-inf) will be obtained from the **AUCINF_obs** parameter calculated by WinNonlin[®]. If the amount extrapolated portion of AUC_(0-∞) is \geq 20%, the estimated AUC_(0-∞) value will be flagged when listed in the report (Listing 26) and will be excluded from statistical summaries of parameter estimates and downstream calculations.

All AUCs will be reported in units of $h*\mu g/mL$.

CL

Clearance (CL) is defined as the volume of plasma completely cleared of drug per unit time and is estimated in trials of an IV-administered drug as the dose divided by the $AUC_{(0-\infty)}$. It will be obtained from the **Cl_obs** parameter calculated by WinNonlin[®]. If the amount extrapolated portion of $AUC_{(0-\infty)}$ is >20%, the estimated CL value will be flagged when listed in the report and will be excluded from statistical summaries of parameter estimates and downstream calculations. CL will be reported in units of L/h.

Vd

Volume of distribution (V_d) will be estimated as the apparent volume of distribution at steady state (V_{ss}) in trials of an IV-administered drug. This value will be calculated using the AUC and area under the first moment curve (AUMC). It will be obtained from the **Vss_obs** parameter calculated by WinNonlin[®]. If the amount extrapolated portion of AUC_(0-inf) is >20%, the estimated V_{ss} value will be flagged when listed in the report and will be excluded from statistical summaries of parameter estimates and downstream calculations. V_d at steady state will be reported in units of L.

AR

The observed accumulation ratio (AR) is defined as the ratio of exposure parameters following multiple dosing. AR will be calculated using AUC₀₋₈ and C_{max} for Dose 1 and Dose 3.

$$AR = \frac{AUC_{0-8, Dose 3}}{AUC_{0-8, Dose 1}}$$
$$AR = \frac{C_{max, Dose 3}}{C_{max, Dose 1}}$$

When λ_Z is estimable, AR will also be estimated using the elimination rate λ_z from Dose 3:

$$AR = \frac{1}{1 - e^{-\lambda_Z \tau}}$$

where τ is the length of the dosing interval, 8 h.

Shift in Tmax

Shift in T_{max} between Dose 1 and Dose 3 will be calculated by the subtraction of T_{max} for Dose 1 from T_{max} for Dose 3. Point estimates of the shift and associated 95% CIs derived from the inversion of the Sign Test will be reported. The 95% CIs will be calculated using the CIPCTLDF option in PROC Univariate.

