4.4. Treatments

4.4.1. Treatments Administered

Each subject will receive three 6 g doses of ZTI-01, administered as a 1-hour IV infusion, every 8 hours for a total 18 g in 3 doses.

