10.4.1. Pharmacokinetic Parameter Summaries for Plasma

Plasma fosfomycin concentrations and summary statistics will be listed and summarized by nominal timepoint for Dose 1 (Table 35) and for Dose 3 (Table 36) and presented graphically:

- Figure 46 will plot all plasma PK profiles plots for Dose 1 and Dose 3 as linear plots and Figure 47 will plot all subject plasma PK profiles plots for Dose 1 and Dose 3 as semilogarithmic plots
- Linear plots of plasma mean concentration curves will be shown in Figure 48 for Dose 1 and Dose 3, with error bars representing +/- 1 standard SD.
- Semi-logarithmic plots of GM plasma concentration curves will be shown in Figure 49 Dose 1 and Dose 3.

PK Estimates for Dose 1 will include C_{max} , T_{max} , T_{last} , $AUC_{(0-8)}$ and will be presented in Table 37. PK Estimates for Dose 3 will include C_{max} , T_{max} , T_{last} , $AUC_{(0-8)}$, $AUC_{(0-last)}$ and $AUC_{(0-inf)}$, λ_z , $t_{1/2}$, CL, and V_d and will be presented in Table 38.

Shift in T_{max} will be summarized for Dose 3 compared to Dose 1 in Table 39 . AR for C_{max} and $AUC_{(0-8)}$ will be summarized for Dose 3 compared to Dose 1 in Table 40.

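### SAP 10.3.1 takes CL and Vss from a Dose 3 area that still contains drug from Doses 1 and 2: CL is biased low, and Vss is biased, usually low

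*SAP*

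**What the plan says.** The regimen in SAP 4.4.1 is: "Each subject will receive three 6 g doses of ZTI-01, administered as a 1-hour IV infusion, every 8 hours". In SAP 10.3.1, AUC0-inf "is defined as the total area under the concentration-time curve from start of infusion for Dose 3", "taken to the limit as the end time becomes arbitrarily large". No AUC0-inf is defined for Dose 1. Clearance "is estimated in trials of an IV-administered drug as the dose divided by the" AUC0-inf and is read from WinNonlin's Cl_obs. Vd is read from Vss_obs, which uses AUC and AUMC.

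SAP 10.4.1 attaches both parameters to the third dose only: the list that opens "PK Estimates for Dose 3 will include" contains CL and Vd, and the Dose 1 list contains neither. SAP 10.2 makes the pre-Dose 3 sample time 0 of the Dose 3 profile.

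The WinNonlin settings in SAP 10.3 list no steady-state option and no subtraction of residual drug. The definitions in 10.3.1 contain no dosing-interval clearance. The same section plans accumulation ratios, one of them with a tau that "is the length of the dosing interval, 8 h". Protocol 11.3 permits data from the first and/or third dose and prescribes no correction.

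**The concern.** Dose divided by AUC0-inf equals clearance only if all the drug under the curve came from the dose in the numerator. The Dose 3 curve starts above zero whenever earlier drug remains, and the SAP expects that, since it plans to measure accumulation. The area then comes from up to three doses and the numerator from one. The moment formula behind Vss_obs rests on the same single-dose condition.

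CL and Vd are named plasma outcome measures (Protocol 3.2, SAP 3.2). The error is systematic: more subjects do not reduce it, and it is larger in subjects with longer half-lives, so it also distorts comparisons between subjects. The report could print a clearance in Table 38 and, in Table 40, an AUC accumulation ratio close to the factor by which that clearance is understated.

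**Working it through.** **Inputs.** 6 g by 1 h infusion every 8 h, three doses (SAP 4.4.1); tau 8 h (SAP 10.3.1); last Dose 3 sample at 12 h (SAP 10.2); lambda_z span of at least 3.0 half-lives (SAP 10.3). The plan states no value of CL, Vss or half-life, so there is no figure to reproduce. Half-life is an assumption and is varied. The dose is read as the single 6 g dose.

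**CL.** Let A be the single-dose AUC0-inf, k = ln2/half-life (h) and f = (e^k - 1)/k, which allows for the 1 h infusion. In a one-compartment model the area left from Doses 2 and 1 after Dose 3 starts is rA, with

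r = f × (e^-8k + e^-16k), so CL_obs/CL = 1/(1 + r).

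At 3 h: k = 0.2310, f = 1.1250, e^-8k = 0.1575, e^-16k = 0.0248. So r = 1.1250 × 0.1823 = 0.2051 and the ratio is 1/1.2051 = 0.830, a bias of -17.0%.

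**Vss.** The carry-over declines with mean time 1/k, which gives

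Vss_obs/Vss = [1/(1 + r)] × [1 - 0.5kr/(1 + r)].

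At 3 h: 0.830 × (1 - 0.5 × 0.2310 × 0.2051/1.2051) = 0.830 × 0.980 = 0.814, or -18.6%.

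| Assumed half-life (h) | r | CL bias | Vss bias |
|---|---|---|---|
| 1 | 0.006 | -0.6% | -0.8% |
| 1.5 | 0.032 | -3.1% | -3.8% |
| 2 | 0.079 | -7.4% | -8.5% |
| 2.5 | 0.139 | -12.2% | -13.7% |
| 3 | 0.205 | -17.0% | -18.6% |
| 3.58 | 0.284 | -22.1% | -23.8% |

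A numerical noncompartmental run at the SAP sampling times (linear up, log down) agrees. CL/Vss bias is -7.2/-7.8% at 2 h, -17.0/-18.4% at 3 h and -22.1/-23.6% at 3.58 h.

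**Why the table stops at 3.58 h.** With points from 1.25 to 12 h, a span of three half-lives needs a half-life of at most 10.75/3 = 3.58 h (11/3 = 3.67 h if the 1 h point is used).

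**Extrapolation rule.** The share of Dose 3 AUC0-inf beyond 12 h is about 2% at 2 h, 6.9% at 3 h and 10.6% at 3.58 h. It reaches about 20% only near 5 h. The exclusion above 20% therefore removes none of these cases.

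**Two compartments.** With terminal half-life 2 to 3.5 h and 50 to 90% of AUC in the terminal phase, CL bias runs from -3.8% to -19.7% and Vss bias from -2.2% to -20.0%. In general Vss_obs/Vss = (1 + rm)/(1 + r)². Here r is the carry-over area divided by the single-dose area. The term m is the mean time of the carry-over area after the start of Dose 3, less half the infusion time, divided by the single-dose mean residence time. The bias turns positive when m > 2 + r. In the runs this needed a terminal phase holding about 30% or less of AUC. One example is +2.9% at 30%, with terminal half-life 3.5 h and distribution half-life 0.3 h. CL stayed low in every run.

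**Dosing-interval clearance.** In the one-compartment model AUC0-8 after Dose 3 equals A(1 - f e^-24k), so Dose/AUC0-8 overstates CL by the factor 1/(1 - f e^-24k). At 3 h this is 1/(1 - 1.1250 × 0.0039) = 1.0044. The CL error is +0.03% at 2 h, +0.4% at 3 h and +1.1% at 3.58 h. The matching Vss error is +0.03%, +0.5% and +1.2%.

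**The case against.** The study tests no hypothesis, and Protocol 11.2 and SAP 5 say that its analyses are not a basis for definitive conclusions. Dose 3 AUC0-8 is planned and listed by subject (Listing 26), so anyone can compute Dose/AUC0-8 afterwards. At a half-life of 1 to 1.5 h the bias is only about 1 to 3% for CL. SAP 10.5 plans a population model with its own parameter estimates, and Protocol 11.3 defers details to a PK analysis plan which, if it is separate from the SAP, is not among the documents here.

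Most of this stands and limits the seriousness. It does not remove the error. SAP 10.3.1 is explicit, and the population model is exploratory and not offered as a replacement for the noncompartmental CL.

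Three stronger readings are tempting, and the documents do not support them:

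- A reader might infer that CL and Vss are both certain to be low. That holds for CL under the stated assumptions. For Vss the direction can reverse, as shown above.
- A reader might infer a bias of 25% or more from a half-life of 4 h. There the span is 10.75/4 = 2.7 half-lives, which fails SAP 10.3. Bias of that size arises only if the looser rule in 10.3.1 governs (correlation above 0.8, no span).
- A reader might infer that the main lung results are compromised. Percent penetration, accumulation ratios, AUC0-8, Cmax and safety use neither CL nor Vss.

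Reading the dose as the 18 g total does not rescue the formula. It gives 3/(1 + r) times the true CL, which is +178% at 2 h and +134% at 3.58 h.

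**Conclusion.** The CL and Vss definitions are wrong as written and should be corrected. The point does not threaten the trial's other results. With the single 6 g dose in the numerator and linear pharmacokinetics, CL is biased low whenever drug remains before Dose 3. Vss is biased, usually low. The size depends on a half-life that the documents do not give. In a one-compartment model it runs from under 1% at 1 h to about 22% (CL) and 24% (Vss) at the longest half-life that meets the SAP 10.3 span criterion.

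**What to change.** For Dose 3, amend SAP 10.3.1 to:

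- define CL as the single administered Dose 3 amount divided by AUC0-8, and state that this single amount is the numerator;
- define Vss = CL × MRT, with MRT = (AUMC0-8 + 8 × AUC8-inf)/AUC0-8 minus half the infusion time (the steady-state NCA setting, tau = 8 h);
- not summarise Cl_obs or Vss_obs from Dose 3;
- label Dose 3 AUC0-inf as including carry-over.

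The cost is SAP wording and one NCA setting, with no new samples. It should be done before final data lock, after which SAP 15 allows no amendment. The downside is small: the formulas treat Dose 3 as close to steady state, which leaves an error of up to about +1.2% at half-lives up to 3.58 h.

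A Dose 1 Dose/AUC0-inf check is best left out, or made conditional on the lambda_z span criterion as well as on extrapolation. Dose 1 sampling ends at 8 h, so from 1.25 h the span criterion passes only at half-lives up to 6.75/3 = 2.25 h, where the bias is smaller.
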